8. STUDY DESIGN

We will use a modified stepped wedge design to evaluate the yield of the HIV-1 RNA testing intervention at 6 public or private health facilities in Kenya, before (1,375 patients) and after (1,500 patients) intervention delivery. This study will be conducted in two phases at each site.

The first phase is the **observation period** in which all testing and treatment will be per Kenyan Ministry of Health guidelines and primary care clinician judgment. Adults seeking care at primary health care clinics who have never been diagnosed with HIV and have a risk score of 2 or higher will be offered participation. HIV testing will only be done if ordered by the primary care clinician. Research procedures in the observation period will consist of a CASI/CAPI at baseline (all participants) and a home visit at 6 weeks (only for those diagnosed with HIV at baseline). The 6-week visit will include a second CASI/CAPI and follow-up on uptake of care and treatment and partner notification. Those who have not yet notified partners will be offered assisted partner notification with standard HIV testing (i.e., standard aPS). Participants found to be HIV negative and those not tested will end their participation at the baseline visit. Those diagnosed HIV positive (estimated to be about 2%) will have 2 visits, baseline and 6 weeks.

In the **intervention period**, there are four major interventions being tested: testing for acute and prevalent HIV infection, aPS using our HIV-1 RNA testing intervention (i.e., enhanced aPS), an ART cohort at KEMRI, and a PrEP cohort at KEMRI. Again, adults seeking care at primary care clinics with no history of HIV and a risk score of 2 or more will be offered enrollment. In the intervention phase, all participants will undergo HIV testing consisting of testing for HIV-1 RNA initially, followed (if positive) by testing with 2 rapid HIV tests per Kenyan HIV testing guidelines. Those who test negative end participation at the baseline visit after the CASI/CAPI as above. Those who test positive (either AHI or prevalent case, estimated to be about 5% for this combined outcome) are offered enhanced aPS and participation in the ART cohort at KEMRI and can accept or decline each one. Those who decline follow-up at KEMRI will end their participation at the 6-week visit (as described above for the observation period), those who accept will be followed at KEMRI for 12 months. Those who test positive will also be offered participation in qualitative interviews, which they may accept or decline without influencing other components.

[figure not shown]
Partners of observation phase HIV-positive participants (i.e., index cases with prevalent HIV infection) will be offered referrals for risk reduction counseling and for HIV care, if infected. Partners of intervention phase HIV-infected participants (i.e., index cases with newly diagnosed acute and prevalent HIV infection) will be offered the HIV-1 RNA testing intervention (as described for participants in the intervention phase above) and enrollment into the KEMRI ART cohort or PrEP cohort based on their test results. If they accept either cohort, they will be followed for 12 months. If they decline and are HIV positive, their participation will end after a 6 week visit as above. If they decline and are HIV negative, their participation will end at the baseline visit after the CASI/CAPI as above. In the intervention period, partners newly diagnosed with HIV through the enhanced aPS intervention will also be offered the enhanced aPS intervention to identify and test their partners. Identified partners of these individuals will be offered the same options as partners of index cases diagnosed in the stepped wedge trial.

Opening of the observational phase at each site will be staggered in 3-month intervals so that no more than 2 sites will be in each phase at any given time. Each phase will last 3-6 months per site with the exception of the first site having only 3 months of observation to allow the study to

proceed more efficiently. Each site is anticipated to enroll approximately 125 participants per 3-month block for a total enrollment of 2875.

We expect to diagnose over two-fold more HIV infections through the HIV-1 RNA testing intervention than are currently diagnosed through PITC. Assisted partner notification should identify at least two-fold more previously undiagnosed individuals for each index case diagnosed than passive referral strategies (the current standard of care), augmenting intervention impact. We also expect that enhanced aPS will identify more previously undiagnosed individuals for each index case diagnosed than delayed standard aPS. Through modelling, we will estimate the impact of this combined intervention on HIV transmission (i.e., HIV infections averted) and clinical outcomes (i.e., deaths averted, DALYs averted) and evaluate the potential cost-effectiveness of this approach under a wide range of estimations. We expect this work to provide invaluable data that will help improve HIV testing and treatment as prevention in sSA.

Our HIV-1 RNA testing intervention network will include both private and public health facilities in a large, peri-urban area (population >100,000) in coastal Kenya (Figure 1). We will select six health facilities (2-4 public, 2-4 private) for inclusion in this study due to their size, central location (within 20 kilometers of one of our two KEMRI Research Clinics, located in Mtwapa and Kilifi), patient volume (>500 patients 18-39 years of age seen over 3 months), availability of HIV rapid testing on-site, availability of a private room for consenting participants, and willingness to collaborate with the research team. Four such facilities (2 private and 2 government) participated in AHI studies conducted by KEMRI in 2013 and 2014.

We have chosen a modified stepped wedge trial design for the following reasons: (1) we predict that the intervention will do more good than harm and (2) for logistical reasons, it is not practical to deliver the intervention simultaneously to all participants. Rolling out the intervention in a staggered fashion will ensure that there is adequate time for individual site preparation and staff training, as well as oversight of study activities. Before study initiation, the six participating clinics will be randomized to observation and intervention periods, as presented below in Figure 2.

Version 1.1 17 July 2018 Page 23 of 137

Figure 2. Stepped Wedge Design at Six Sites

. iguit zi etoppeu rreuge zeoigii ut eix eitee								
Clinic	0-3	4-6	7-9	10-12	13-15	16-18	19-21	22-24
Site 1	0	_						
Site 2	0	0	1	I				
Site 3		0	0	ı	ı			
Site 4			0	0	ı	ı		
Site 5				0	0	I	I	
Site 6					0	0	ı	ı
N enrolled	250	375	500	500	500	375	250	125

I = intervention period, N = number, O = observation period

Randomization will be performed using a random number generator to assign each clinic to one of the six positions, with stratification by facility type (public vs. private). Due to practical limitations, allocations will be unblinded. We will recruit 125 participants per clinic per 3-month time block, for 2,875 total participants (1,375 in the observation period and 1,500 in the intervention period) in the HIV-1 RNA testing intervention. By the end of the trial, each facility will have undergone an observation period of 3-6 months and received the intervention for 3-6 months. Thus, each health facility or "cluster" will act as its own control, with comparison of those patients enrolled during the observation period to those patients enrolled during the intervention period. Using this design, we can model the effect of time on the intervention, adjusting for temporal variations in HIV incidence [56, 57].

Version 1.1 17 July 2018 Page **24** of **137**

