Version 1.1 17 July 2018 Page 11 of 137

Secondary Objectives:

- Linkage to care: To determine the feasibility, acceptability, and uptake of offering immediate linkage and treatment to all newly diagnosed HIV-infected patients in the intervention period, comparing this approach to standard care.
- Partner testing: To determine the feasibility, acceptability, and uptake of aPS for partner identification and testing, comparing enhanced aPS with HIV-1 RNA testing in the intervention period to passive referral followed by delayed aPS with standard HIV testing in the observation period.
- Impact and cost-effectiveness: To model the potential impact of
 the HIV-1 RNA testing, linkage, immediate treatment, and aPS
 interventions on the Kenyan HIV epidemic, in terms of
 incremental costs per HIV infection averted, death averted, and
 disability-adjusted life-year (DALY) averted, using data on
 standard care outcomes from the observation period and data
 on intervention outcomes from the intervention period.

Exploratory Objectives:

- Barriers and facilitators: To conduct qualitative in-depth interviews with up to 60 newly diagnosed prevalent and AHI patients and seronegative partners in discordant relationships to gain insights into intervention uptake, including barriers and facilitators to ART or PrEP uptake and adherence in these groups.
- Staff views: To conduct interviews or focus groups with up to 60 individuals who work in the 6 health facilities where the trial will take place (up to 10 participants per facility), to obtain their views on HIV-1 RNA testing and the research carried out at the facility, including challenges to intervention scale-up.

Endpoints:

Primary Endpoints:

HIV-1 RNA testing intervention: Proportion of participants with the following outcomes in the observation and intervention periods:

- tested for HIV infection;
- newly diagnosed with prevalent HIV; and
- newly diagnosed with AHI (0 in the observation period).

Secondary Endpoints:

Linkage to care: Proportion of newly diagnosed patients with the following outcomes in the observation and intervention periods:

- successfully linked to care by week 6; and
- initiating ART by week 6 following HIV diagnosis.

Version 1.1 17 July 2018 Page 12 of 137

For ART cohort participants (intervention period only) we will also assess:

- proportion initiating ART by month 3 following HIV diagnosis;

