9. STUDY POPULATION

9.1. Inclusion Criteria for the Stepped Wedge Trial

The stepped wedge trial of the HIV-1 RNA testing intervention will be carried out in 6 outpatient health facilities in an area with a high prevalence of sex work, among both men and women. While sex work and other high-risk sexual behaviors are not part of the eligibility criteria for the study, data on sexual risk behaviors will be collected from all eligible patients.

The eligibility criteria target young adults, in whom HIV incidence is highest in Kenya, and focuses on symptoms and signs compatible with AHI, identified through our previous work (reviewed in Section 6.4).

Eligibility criteria for participation in the stepped wedge trial include:

- age from 18-39 years;
- · not previously diagnosed with HIV infection; and
- a score ≥2 on our risk score algorithm to identify persons at higher risk for AHI, with scoring as follows:
 - o age 18-29 years (1),
 - o fever (1),
 - o fatigue (1),
 - o body pains (1),
 - o diarrhea (1),
 - o sore throat (1), and
 - o GUD (3).

Eligibility criteria for partners of newly diagnosed cases with prevalent or acute HIV include:

- age over 18 years; and
- not previously diagnosed HIV infection.

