 - During the observation period, we will use a consent (Consent 1) that focuses on the CASI/CAPI collection of data, collection of data on tests performed during the clinic visit, and permission for a follow-up visit at 6 weeks if newly diagnosed with HIV infection by the clinic.

Version 1.1 17 July 2018 Page 29 of 137

¹ The script for this video was reviewed and approved by our three ethical review boards.

During the intervention period, we will use a consent (Consent 2) that informs
participants that diagnostic testing is offered as part of the study and may reveal a
diagnosis of acute or prevalent HIV infection. The intervention period consent will
therefore focus on testing for acute and prevalent HIV infection, CASI/CAPI
collection of data, and permission to discuss results and further research
participation options with individuals who are newly diagnosed with HIV infection
by the research team.

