Assisted partner	Assisted partner services consent	N=75 / 6 health facilities or KEMRI	
notification	for all newly diagnosed	clinic	
4. Partner testing	Partner testing consent	N=300 / partner home or KEMRI	
		clinic	

Version 1.1 17 July 2018 Page **70** of **137**

5. Immediate	Cohort follow-up for HIV positive	N= 75 (and unknown HIV infected
treatment	patients and partners	partners) / KEMRI clinic
6. PrEP	Cohort follow-up for HIV negative (with PrEP)	N=75 / KEMRI clinic
7. Qualitative	Personal interview	N=60 / KEMRI clinic
8. Staff	Personal interview or focus group	N=60 / 6 health facilities

- Each ICD document will describe the purpose of the specific component of the study described, the procedures to be followed, and the risks and benefits of participation.
- During the consent process with each ICD, staff will explain the purpose and design of the specific study component, taking care to inform patients that participation is voluntary and will not influence their access to care or any other services to which they are entitled.
- Consent forms will be available in Swahili and English, and a copy will be given to each
 participant in the language of his or her choice.
- If an individual is illiterate, we will explain all procedures, risks, and benefits and offer the
 option of having a friend, family member, or paid consultant who is not a member of the
 research staff be present to further explain the study.
- Written informed consent will be obtained from all participants; persons incapable of consenting are excluded.
- Potential participants who would like to take additional time to consider their enrolment will be encouraged to do so.
- The informed consent process will be conducted by staff members trained in the ethical treatment of human subjects. This process involves presenting a detailed verbal description of the study as described on the printed, IRB-approved consent form.
- Staff will emphasize that participation is voluntary, and that participants can refuse to answer
 any question or undergo any procedure or can discontinue participation at any time without
 penalty.
- Participants will be informed of the procedures for ensuring confidentiality, including use of
 unique non-personally identifying ID numbers instead of names on research materials, and the
 maintenance of data in encrypted computer databases and locked filing cabinets in locked
 rooms.

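### The primary endpoint 'tested for HIV' counts only enrolled participants, so in the intervention period it will show delivery to enrolees rather than uptake among eligible patients

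*Combined protocol and SAP*

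**What the plan says.** **Endpoint.** Section 5 (Primary Endpoints) defines the outcomes as: "HIV-1 RNA testing intervention: Proportion of participants with the following outcomes in the observation and intervention periods". The first outcome listed is having been tested for HIV. Section 15.1, headed HIV Testing Uptake and Diagnoses, compares it between periods.

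**Intervention period.** Section 8: "In the intervention phase, all participants will undergo HIV testing consisting of testing for HIV-1 RNA initially". Section 11.1.1 says Consent 2 informs "participants that diagnostic testing is offered as part of the study and may reveal a" diagnosis of acute or prevalent infection, and that this consent will "therefore focus on testing for acute and prevalent HIV infection, CASI/CAPI" data and later research options.

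**Observation period.** Section 11.1.1 describes "a consent (Consent 1) that focuses on the CASI/CAPI collection of data, collection of data on tests performed during the clinic visit", with a six-week visit for those newly diagnosed. Under Section 8 a test is done only if the clinician orders one, and: "Participants found to be HIV negative and those not tested will end their participation at the baseline visit". Untested people are thus participants and stay in the denominator.

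**Before enrolment.** Section 11.1.1 places the invitation and consent ahead of any HIV test. Form 1 (Section 21.6) lists not wanting an HIV test among the reasons for not enrolling. Willingness to test is not on the list that Section 9.1 opens with "Eligibility criteria for participation in the stepped wedge trial include", but Section 9.2 excludes anyone unwilling to participate.

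**Planned reporting.** Section 15.1 tallies refusal reasons among eligible patients, compares refusers with consenters, and gives the proportions screened, eligible and enrolled. None of this is stated to be by period.

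**The concern.** What a patient agrees to at enrolment differs between periods. A patient who does not want an HIV test can join the observation period without taking one and is then counted as untested. In the intervention period that patient has reason to decline, and then appears in no denominator. A proportion tested close to 100% would follow largely from who enrols.

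At stake is the reading of a primary endpoint. Taken as uptake, it would hide any refusal that occurs before enrolment. The diagnosis comparison may carry the same selection. Section 15.4 takes the intervention's impact on diagnosis from study data, so the impact and cost-effectiveness model inherits the same enrolled-only basis.

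**Working it through.** **1. The plan's own figure.** Inputs from Section 14 and Figure 2: 2.0% versus 5.0% diagnosed, k = 0.25, six sites, 125 participants per site and block, 11 observation and 12 intervention cells (1,375 and 1,500 participants). Method: weighted least squares for a stepped wedge with block effects and a random site intercept, variance at the mean of the two proportions, two-sided 5% level (sidedness assumed). This gives 93.0%, as stated. All eight table rows reproduce to within 0.1 percentage point (computed 94.4, 82.2, 93.0, 79.9, 91.4, 77.3, 89.4, 74.6%). The power refers to participants and is not in question.

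**2. The same reluctant patient in each period.**

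| Step | Observation | Intervention |
|---|---|---|
| Asked to consent to | Survey and record collection (11.1.1) | HIV testing and survey (11.1.1) |
| Test after enrolment | Only if the clinician orders it (8) | All participants (8) |
| Enrols, not tested | Counted as untested | Counted as untested |
| Declines because of the test | Not counted | Not counted |

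The counting rules are the same. What differs is the incentive to take the last row. That is an inference from procedures: Form 1 serves both periods, and no refusal figure by period or reason is given.

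**3. Illustration.** Let rI and rO be the shares, among eligible patients otherwise willing to enrol, who decline because of the test in the intervention and observation periods. All values are assumptions. Return these patients to the denominator as not tested and not diagnosed.

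- Patients returned: N × r/(1 − r). Intervention: 1,500 × 0.05/0.95 = 79; 1,500 × 0.10/0.90 = 167; 1,500 × 0.20/0.80 = 375. Observation at rO = 5%: 1,375 × 0.05/0.95 = 72.
- *Tested*, intervention: at most 1 − rI.
- Diagnosed: 5% × (1 − rI) and 2% × (1 − rO). Check at rI = 20%: 75/(1,500 + 375) = 4.0%.
- Ratio: 2.5 × (1 − rI)/(1 − rO).

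| rI | *Tested*, at most | Diagnosed, intervention | Ratio, rO = 0 | Ratio, rO = 5% | Ratio, rO = rI |
|---|---|---|---|---|---|
| 5% | 95% | 4.75% | 2.38 | 2.50 | 2.50 |
| 10% | 90% | 4.50% | 2.25 | 2.37 | 2.50 |
| 20% | 80% | 4.00% | 2.00 | 2.11 | 2.50 |

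Only a difference between periods moves the ratio. If refusal were higher in the observation period the ratio would rise: rI = 5% and rO = 10% give 2.5 × 0.95/0.90 = 2.64. The corresponding ratio for *tested* cannot be computed, because the observation-period testing share is not given.

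**4. Outer limit on reach.** Section 14 expects 50%-80% of eligible patients to accept participation. So 1,500 participants imply 1,500/0.80 = 1,875 to 1,500/0.50 = 3,000 eligible patients, with 375 to 1,500 not enrolled. The study test would then reach 50%-80% of eligible patients. This counts refusals for every reason, so it limits the loss from test refusal without estimating it.

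**The case against.** **The enrolled-only denominator is the stated one.** The endpoint is a proportion of participants, Section 8 compares enrolled patients, and the study is a proof of concept. That stands, and it is why the primary analysis should not change. What remains is that the heading of Section 15.1 invites a reading as uptake that this denominator cannot support.

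**Unwillingness to participate is a written exclusion, and refusals are already tallied.** Both are true (Sections 9.2 and 15.1). The gap is narrow: nothing is stated to be by period, and *tested* is never set against eligible patients. Covariate adjustment for baseline imbalance in the secondary models may partly address selection in the diagnosis comparison, but it cannot restore people who never enrolled.

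**Participants can still refuse after consent.** Testing is described as offered, and Section 17.3 lets participants refuse "any question or undergo any procedure or can discontinue participation at any time without" penalty. *Tested* may therefore fall somewhat below 100%. Such people correctly stay in the denominator as untested, so this does not reach refusal before enrolment.

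**Stronger readings that the documents do not support.** A reader might infer that test refusers are lost only or mainly in the intervention period; the two consents make this plausible, but no figure shows it. A reader might apply the 50%-80% acceptance to the intervention period alone and conclude that the diagnosis ratio falls to 1.25-2.0 (2.5%-4.0% against 2%). Section 14 gives one range for the study, not split by period or reason; applied equally, with non-participants counted as undiagnosed, it leaves the ratio unchanged. Nor is universal versus clinician-ordered testing a flaw: it is the intended contrast.

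**Conclusion.** The point holds as one of interpretation and reporting, and should be fixed before analysis. In the intervention period *tested* will be near 100% largely by construction. It measures delivery to patients who enrolled for testing, not uptake among eligible patients.

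Whether the diagnosis comparison is also affected, by how much and in which direction, cannot be determined: the documents give neither refusal by period nor HIV prevalence among refusers. The ratios of 2.4-2.0 rest on assumed refusal of 5-20% confined to the intervention period and on counting refusers as undiagnosed; they are not estimates. The planned power stands. Confidence is medium, because greater loss in the intervention period is inferred from procedures.

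**What to change.** In Section 15.1:

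1. Keep the enrolled-only analysis as primary. Describe intervention-period results as *among patients who enrolled for testing*, and do not interpret *tested* as uptake.
2. From Form 1, report by period and facility the numbers eligible, not enrolled because they did not want an HIV test, not enrolled for other reasons, and enrolled; add the number tested from the trial data.
3. Prespecify one sensitivity analysis of *tested* and of combined diagnosis, with the same GEE model and the same rule in both periods. It returns to the denominator eligible patients whose only recorded reason for not enrolling is not wanting an HIV test, counted as not tested and not diagnosed. Participants who refuse after consent stay in as untested. Describe the result as the lowest value for each period under this rule, not as a bound on the ratio.

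In Section 15.4:

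4. Name test refusal among the parameters varied in the cost-effectiveness sensitivity analyses.

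The cost is plan wording and one extra analysis. Form 1 already carries date, facility and reasons, and every screening outcome is recorded on it.

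The downsides should be stated with the results. Screening data are verified only after written consent (Section 9.3), so age and HIV status of non-enrolled patients are unverified. Some of them may still be tested on a clinician's order, since declining the study does not affect access to testing (Section 11.1.1). Screenees are not identified, so double counting is possible. Eligibility is unknown for those who refuse screening itself. The effect may look smaller. The analysis addresses test refusal only, not other differences in recruitment such as the explainer video shown only in the intervention period.

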15. DATA ANALYSIS

15.1. HIV Testing Uptake and Diagnoses

We will compare the age and sex of individuals who accept vs. refuse screening, using Student t and Chi-square tests. In addition, we will tally reasons for refusal to participate among those eligible, and compare eligible individuals who refuse vs. consent to study enrolment, using Chi-square or Fisher exact tests for categorical variables and Student t tests or Mann-Whitney U tests for continuous variables. Proportions of individuals who accept screening, are determined eligible, and enroll will be presented, with exact binomial CI.

We will compare the proportion of patients with the following outcomes in the observation and intervention periods: (1) tested for HIV infection; (2) newly diagnosed with prevalent HIV infection (i.e., HIV seropositive); (3) newly diagnosed with AHI. Because we expect 0 AHI cases in the observation period, we will use a combined outcome (i.e., newly diagnosed acute or prevalent HIV-1) to model the effect of the intervention, so that models will converge. We will conduct analyses on the individual-level data, using log-binomial generalized estimating equation (GEE) models to account for clustering by health facility. We will use a small-sample variance correction to handle the small number of clusters [63]. Models will include indicator variables for calendar time period to control for trends in HIV incidence in the study area.

We will compare baseline characteristics between individuals in the observation and intervention groups, using Chi-square or Fisher exact tests for categorical variables and Student t tests or Mann-Whitney U tests for continuous variables. Where imbalances are identified, we will control for these potential confounders in secondary analyses using GEE models as above. We will also conduct exploratory analyses to identify predictors of the combined outcome (i.e., newly diagnosed acute or prevalent HIV-1) in the intervention group, including age, sex, marital status, symptom or symptoms reported, sex of partners, number of partners, condom use, transactional sex work, and other risk behaviors. We will test for interactions between the intervention and other variables such as sex, and will present stratified analyses if meaningful interaction is observed. In analyses in which multiple null hypotheses are tested, p values will be adjusted using the Holm–Bonferroni method.

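### Section 8 stratifies the clinic order by facility type without saying how positions are shared between types, and the primary model in 15.1 leaves that factor out

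*Combined protocol and SAP*

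**What the plan says.** On the draw, section 8 of the combined protocol and SAP states: "Randomization will be performed using a random number generator to assign each clinic to one of the six positions, with stratification by facility type". Figure 2 gives each position to one clinic. The number of clinics per type is left open: "We will select six health facilities (2-4 public, 2-4 private) for inclusion in this study due to their size". The text gives no block structure and no rule for which positions each type may take.

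On the analysis, section 15.1 specifies a log-binomial GEE clustered on facility with a small-sample variance correction. "Models will include indicator variables for calendar time period to control for trends in HIV incidence in the study area". Calendar period is the only adjustment named for the primary model, and no working correlation is stated. Baseline characteristics found to be imbalanced between periods are adjusted for in secondary analyses only. Facility type is not named there either.

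Section 8 also says that each facility serves as its own control, but the 15.1 model contains no facility effects.

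**The concern.** Ordering clinics at random within each type does not spread the types over six single-clinic positions. That needs a prior step allotting positions to types, and none is written. On that reading, all clinics of one type could cross over first.

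Once calendar blocks are in the model, the information on the intervention comes from blocks in which some facilities are in observation and others in intervention. Those are comparisons between different facilities. If early positions are mostly one type, part of any public-private difference in undiagnosed HIV or in provider-initiated testing is attributed to the intervention. Facility type is the factor the design itself picked out as worth balancing, yet the primary model does not use it.

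**Working it through.** **Inputs.** Figure 2 has 23 clinic-by-block cells. Site 1 has one observation and two intervention blocks, as the enrolment row requires; sites 2 to 6 have two of each. Section 8 gives the cell size ("We will recruit 125 participants per clinic per 3-month time block") and the totals ("for 2,875 total participants (1,375 in the observation period and 1,500 in the intervention period"): 11 × 125 = 1,375 and 12 × 125 = 1,500. Section 14 gives 2% vs 5%, alpha 0.05 and k = 0.25. The public-private difference is not in the documents and is treated as an assumption.

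**1. Reproducing the plan's power.** I used weighted least squares on the 23 cells with fixed block effects, cell variance p(1−p)/125 and facility variance (k·p)², where p = (0.02 + 0.05)/2 = 0.035. The standard error is 0.00872, so power = Φ(0.03/0.00872 − 1.96) = 93.0%, as printed. All eight entries in the section 14 table reproduce within 0.1 point.

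**2. Share of a type difference entering the estimate (working independence).** This is the coefficient on intervention when a 0/1 type indicator is regressed on block indicators and intervention. It equals Σ(x − x̄ of the block)·type / Σ(x − x̄ of the block)².

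- Only blocks 2 to 6 contain both conditions. Their sums of squares are 2/3, 1, 1, 1 and 2/3, total 13/3.
- Numerators: site 1, 2/3 + 1/2 = 7/6; site 2, −1/3 + 1/2 + 1/2 = 2/3; site 3, −1/3 − 1/2 + 1/2 + 1/2 = 1/6. Sites 4, 5 and 6 are −1/6, −2/3 and −7/6 by symmetry.
- Dividing by 13/3 gives 7/26, 4/26, 1/26, −1/26, −4/26 and −7/26. The share for any order is the sum over the positions held by one type.

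| Split and draw | Maximum | Mean absolute |
|---|---|---|
| 3/3, unrestricted (20 orders) | 12/26 = 46.2% (positions 1-3 vs 4-6; 2 orders) | 5.2/26 = 20.0% |
| 2/4, unrestricted (15 orders) | 11/26 = 42.3% | 4.8/26 = 18.5% |
| 3/3, one of each type in 1-2, 3-4, 5-6 | 4/26 = 15.4% | 2/26 = 7.7% |
| 2/4, types split equally between 1-3 and 4-6 | 6/26 = 23.1% | – |

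The signed mean over unrestricted orders is 0. With exchangeable weights the 3/3 maximum is 43.2% at k = 0.25, and 44.3% to 40.4% for k from 0.20 to 0.35.

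**3. Effect on the risk ratio.** A log-link binomial fit to expected values, true RR 5%/2% = 2.50, one type in positions 1-3 and the other in 4-6. The type ratios are assumed:

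| Type ratio | Estimate, higher-rate type first | Estimate, higher-rate type last |
|---|---|---|
| 1.25 | 2.77 | 2.26 |
| 1.5 | 3.00 | 2.08 |
| 2.0 | 3.38 | 1.83 |

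Adding facility type returns 2.50 in every pattern tried.

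**4. Cost of the covariate if the types do not differ (k = 0.25, 2% vs 5%).**

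- Paired 3/3 orders: variance up 0.9% on average, power 92.8% (92.4% to 93.0% by order).
- Unrestricted orders: variance up about 13% (3/3) or 12% (2/4) on average.
- 3/3 order 1,2,4 vs 3,5,6: variance up 27%, power 86.4%.
- Types fully separated (1-3 vs 4-6): variance up 72%, power 74.7%.

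**The case against.** **The phrase may already mean a balanced draw.** Section 8 is silent on method; it does not describe an unrestricted draw. That stands. A reader might infer that six single-clinic positions cannot be stratified at all, but step 2 shows that blocking positions works. The gap is that no method is written down.

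**46% is an extreme.** It needs an unrestricted draw, a 3/3 split, complete separation of types and working independence. In 12 of the 20 orders the share is already at or below 15.4%. This stands too, though the other 8 of 20 exceed 20%. Nor do the documents support reading this as systematic bias of the design, because the share averages zero over the randomisation.

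**Power.** One might infer a large power loss by assuming, say, a two-fold public-private ratio. In a 3/3 split that ratio alone implies a between-facility coefficient of variation of (2 − 1)/(2 + 1) = 0.33. Adding a residual k of 0.15 to 0.25 gives √(0.33² + 0.15²) = 0.37 to √(0.33² + 0.25²) = 0.42, above the largest value in the plan's table (0.35). The plan's k would already include any type difference. The documents therefore do not support a claim of that kind.

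**Secondary adjustment exists.** Section 15.1 could admit facility type after imbalance is seen. That is a partial remedy only: it is not named, it depends on the data, and it leaves the primary estimate unchanged.

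**Conclusion.** The point holds in a limited form. The method of stratification is unstated and the primary model omits the stratification factor. If the draw does not balance positions, the realised order carries on average 20% (3/3) or 18% (2/4) of any public-private difference into the estimate, and at worst 46% or 42%, under working independence. This is bias conditional on the order drawn, and extra variance over orders. The size in risk-ratio terms depends on a public-private difference that the documents do not give; the ratios in step 3 are illustrative. With a single realised order of six clusters, averaging to zero over orders is little comfort for the result that is reported. The matter should be settled before outcome data are available.

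**What to change.** 1. In section 8, state the number of clinics of each type and how positions are allotted. For 3/3, put one of each type in positions 1-2, 3-4 and 5-6, in random order within each pair (share at most 15%). For 2/4, split both types equally between positions 1-3 and 4-6 (at most 23%).
2. In section 15.1, name facility type as a covariate in the primary GEE and state the working correlation.

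**Cost.** The text change is small, although fixing the split also constrains site selection, which is now open at 2-4 per type. With paired 3/3 positions, variance rises about 1% (power 93.0% to about 92.8% at k = 0.25). One cluster-level degree of freedom is lost; if it falls from 5 to 4, the t multiplier goes from 2.57 to 2.78, about 8% larger, which the power figures do not include.

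**If an unblocked order is already drawn**, do not add the covariate without looking at its price: about 12-13% in variance on average, up to 72% (power about 75%) when types are fully separated. Restate power for the actual order, and decide before outcome data whether the adjusted model is primary or a named sensitivity analysis. Full facility fixed effects would also remove the problem, but power falls to about 49% in the same calculation.
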